TLC FIT	Teens Living with Cancer – Fitness Improvement Training
AYA	Adolescent and Young Adult
CINJ	Cancer Institute of New Jersey
LITE	Long-term, Information, Treatment effects, and Evaluation program
IRB	Institutional Review Board
NCI	National Cancer Institute
NIH	National Institutes of Health
PI	Principal Investigator
PA	Physical Activity
HRQOL	Health-Related Quality of Life
CCSS	Childhood Cancer Survivor Study
SCT	Social Cognitive Study

The K07 is a 5-year training grant and part of the training plan is for [name] to learn how to design and implement the studies outlined in the proposal (i.e., development of a mobile application “app” and evaluation of a behavioral intervention incorporating the newly developed app). In this application, we have described the general procedures of the project but the exact project details will be finalized during the grant period. We will modify the protocol on an ongoing basis as needed to reflect the development of project materials (i.e., mobile app) or any changes in procedures. We will obtain IRB approval for all study procedures and materials prior to their utilization in the project.

1. Purpose/Specific Objectives

The goal of this project is to develop and evaluate the feasibility of “TLC FIT” (Teens Living with Cancer Fitness Improvement Training), a technology-enhanced fitness program for adolescent and young adult (AYA) survivors of childhood cancers. Advances in treatment have fortunately led to a growth in the number of childhood cancer survivors in the US. Unfortunately, these survivors are at-risk for negative late effects from treatment, including cardiovascular disease and early death. Physical inactivity can exacerbate these risks. Adolescent survivors of childhood cancers in particular have reported significant declines in physical activity that persist following treatment. In preliminary work, we designed an eight-session group-based fitness program for AYA survivors using social cognitive theory. This program incorporated the FitBit, a novel commercially available electronic accelerometer, which allowed for self-monitoring of activity. The FitBit also provided an internet-based website for social networking among participants. The program was feasible and acceptable to participants, and they suggested lengthening the program to 12 weeks. Further, participants reported low levels of engagement with the FitBit website and a strong interest in on-the-go access to program materials outside of weekly group sessions. Therefore, the next step is to significantly enhance the technology by creating a cancer-specific smartphone application (app) that motivates participants to engage in and *sustain* behavior change. *Phase 1* of this project involves the development of the mobile app. Following app development and validation, in *Phase 2* we will conduct a randomized pilot trial ($n = 88$) of TLC FIT to evaluate feasibility and effectiveness.

1.1 Primary Objectives

Aim 1: Develop and evaluate the usability of cancer-specific and motivational tools in the mobile app (Phase 1).

AYA survivors will help design the functionality requirements for the initial prototype. An experienced app development company will program the app with identified tools such as goal setting, self-monitoring, exercise instructions, and social networking. Usability testing will be conducted in an iterative manner with AYA survivors, refining the app based on user feedback (total $n = 20$).

Aim 2: Evaluate the feasibility of the technology-enhanced (electronic accelerometer + app + 8 weekly group sessions) fitness program in a pilot randomized clinical trial (Phase 2).

Hypothesis 1: AYAs will agree to participate in the program, demonstrate engagement in the program via > 80% attendance at group-based sessions, and use one or more components of the app at least weekly.

1.2 Secondary Objectives

Aim 3: Determine the effectiveness of the technology-enhanced fitness program on participants' cardiorespiratory fitness and muscular fitness.

Hypothesis 2: Participants in the intervention group will demonstrate greater improvement in cardiorespiratory fitness (objective submax treadmill test) and muscular fitness (objective 10-repetition tests) from baseline than wait-list control participants at the post-intervention assessment.

Aim 4: Examine the effects of the program on secondary outcomes of health-related quality of life (HRQOL) and fatigue.

Hypothesis 3: Participants in the intervention group will demonstrate greater improvement in HRQOL (PedsQL Generic Core Scale) and fatigue (PedsQL Multidimensional Fatigue Scale) from baseline than the wait-list control group at the post-intervention assessment.

2. Background and Significance

Physical inactivity is a significant problem for childhood cancer survivors. Advances in therapy have resulted in survival rates of almost 80% for children diagnosed with cancer,¹ and there are now over 350,000 childhood cancer survivors in the US.² These survivors are at risk for negative late effects from treatment, and almost two-thirds will develop at least one chronic health condition.^{3,4} Premature cardiovascular morbidity and mortality, physical inactivity, and obesity are serious concerns.⁵⁻¹⁰ A sedentary lifestyle is a risk factor for health problems and may exacerbate late effects of treatment, increasing the risk of cardiovascular disease, osteoporosis, and early mortality.⁶ Physical activity (PA) is well known to reduce risk for cardiovascular disease and early mortality.^{11,12} In healthy children and adolescents, increased PA is associated with benefits such as improved cardiorespiratory fitness, muscular fitness, bone health, and body composition.¹³ PA is also positively associated with quality of life.¹⁴⁻¹⁶ Because survivors of childhood cancers are inherently at risk for serious late health effects, programs to promote PA are especially important for this population. A recent systematic review of PA in childhood cancer survivors indicated the need for evidence-based behavioral interventions to promote physical activity.¹⁷ Despite a need and interest in PA promotion programs for this group,¹⁸ there are very few controlled studies of PA interventions for adolescent and young adult (AYA) survivors.^{10,16,19} The proposed work will evaluate the effectiveness of a highly-engaging technology-enhanced PA intervention program designed specifically for AYA survivors.

Adolescents and young adults (AYAs) are especially important to target. AYA survivors are recognized as a unique group that warrants further attention to treatment and survivorship issues as they transition from pediatric to adult health care settings.²⁰ There are many barriers to successful transition, and AYA survivors may be lost to follow-up or receive inadequate care if the transition is not successful,²¹ reducing opportunities for counseling regarding the benefits of PA and other health promotion behaviors. A report from the Childhood Cancer Survivor Study (CCSS) indicated that adult survivors of childhood cancers are less likely to meet CDC

guidelines for PA and more likely to report an inactive lifestyle than siblings.²² Because health behaviors adopted by AYAs are likely to be “carried over” into adulthood,^{19,23} intervention during this time period is likely to improve PA trajectories into adulthood and reduce disparities between adult survivors and siblings. Further, intervening earlier may produce better outcomes, as AYAs are unlikely to have chronic de-conditioning like older adults and more likely to have plasticity of body tissues.²⁴

Factors associated with physical activity in AYA survivors of childhood cancers. As

pictured in Figure 1, treatments for childhood cancers, including radiation and various chemotherapies (e.g., anthracyclines, vincristine), can lead to adverse acute and long-term health effects, including deficits in fitness and health-related quality of life (HRQOL).^{6,25} These adverse changes reduce AYAs’ beliefs in their abilities to engage in physical activity (self-efficacy for PA) and may prompt reduced support for PA from parents and peers, leading to reductions in physical activity. Sedentary habits can exacerbate functional deficits and fatigue, becoming a self-perpetuating cycle.²⁴ Social Cognitive Theory (SCT)^{26,27} proposes that behavior is reciprocally influenced by multiple personal/cognitive and environmental/social factors. Emphasis is placed on self-efficacy, or belief in one’s capability to conduct the intended behavior (physical activity) and overcome perceived barriers to a behavior, and outcome expectancies, or beliefs that the behavior will have the desired effect (e.g., improve fitness). Social modeling, or learning through observation of others’ experiences, and social support for the activity are also key components. For AYA survivors, self-efficacy and support for PA are critical components to target. Specifically, self-efficacy is positively associated with physical activity in young adult cancer survivors and healthy AYAs.²⁸⁻³⁰ Greater family and peer support for PA have been associated with increased PA.³¹⁻³⁶ Peer support is particularly important for adolescents.^{35,36} Certain demographic factors, including male gender and younger age, are also consistently correlated with PA.^{22,30,32} The proposed intervention is guided by Social Cognitive Theory and will evaluate the role of self-efficacy and support for PA in AYA survivors of childhood cancers. What is learned will contribute to the broader understanding of health promotion for AYA survivors.

[figure not shown]

Figure 1. Model of cancer-related deficits and social cognitive determinants of physical activity (PA)

2.1 Supporting Data and Rationale. Guided by Social Cognitive Theory, we developed an 8-week group intervention with four primary components: (1) educational modules, (2) physical exercise, (3) goal-setting and self-monitoring, and (4) social support. Each session was detailed in a manual. This program incorporated the “FitBit,” a small electronic accelerometer that uploads data wirelessly to a personalized account for monitoring PA. Because participants could modify their behavior based on viewing activity levels using FitBit, this technology was used as part of the intervention but not as an outcome measurement. Participants met weekly and provided social support in-person as well as through a private forum on the FitBit website.

Nine participants completed baseline and post-intervention measures (100% retention). On average, participants attended 6 out of 7 weekly exercise sessions (the 8th week was an

Protocol Version 1.9 – 8/30/2017
CINJ# 131323

assessment only). There were no serious adverse events during the study. Our preliminary work demonstrated feasibility in enrolling participants, retaining participants, and completing the various assessment measures. There was evidence of improvement in time spent in physical activity, muscle strength, health-related quality of life, and fatigue that warrants further study. Participants reported high satisfaction with the program and FitBit. Despite increases in PA by actigraphy, we did not see large improvements in cardiovascular fitness (Mile Run/Walk). As a result, we will modify session structure to devote more attention to aerobic training. Further, participant feedback indicated interest in more fitness sessions (12 instead of 8), increased intensity of cardiovascular exercises, and additional structure to individualized exercise plans outside of session. These suggested refinements to the program are included in this proposed study.

Interest in mobile app development. Although participants reported that the FitBit website and group forum were easy to use, they reported logging in only “rarely” or “sometimes” because going to a computer to log in was a barrier. Participants are more likely to engage if access is immediate and available wherever they are. Hence, a primary goal of developing a mobile app is to increase engagement with study materials outside of the weekly sessions. In response to a survey, six out of 9 (67%) participants expressed “quite a bit” or “extreme” interest in trying an app to promote PA. Of the three who did not express high levels of interest, two indicated that they were uninterested because they do not currently own a smartphone, but expressed high interest if they were to be given a smartphone or iPod touch as part of the intervention. Of those who expressed an interest, participants indicated a high level of interest in functions like messaging/texting with a coach, tracking calories consumed and burned, goal setting, goal tracking, and messaging/texting with other survivors. Additional suggested features included a list of exercises for individual workouts, making steps and activities viewable by all group members for motivation and support, and awarding a weekly prize or badge for being the most active.

3. Participating Institutions

Project planning, recruitment, data collection, data management, and data analyses will take place at the Rutgers Cancer Institute of New Jersey. Because this is a K07 award, [name] has selected a team of mentors to provide training in their respective areas of expertise and facilitate the successful completion of the proposed project. ITX Corporation will program the app based on the requirements defined by the research team. They have completed necessary paperwork to partner with Rutgers Cancer Institute of New Jersey researchers on this project. Hackensack University Medical Center will participate as a site with IRB approval from the HackensackMeridian IRB.

4. Experimental Design and Methods

Overall Study Design: The primary goal of the proposed study is to develop and evaluate the feasibility and effectiveness of TLC FIT, a technology-enhanced intervention to promote physical activity in AYA childhood cancer survivors. Phase 1 includes development and usability testing of the smartphone application (Aim 1). Employing user-centered design methods,^{37,38} we will work with AYA survivors (“end users”) to design and refine prototype versions of the app. Technology consultants (contract to be determined) will create the app using theoretically-based features identified as desirable in our previous work. We will recruit a total of 20 AYA survivors to assist in the development and usability testing of the mobile app. This will be an iterative process such that AYAs will give ideas about desired features, assist in critiques of prototypes, and later test a working version of the product. Next, in Phase 2 we will conduct a pilot RCT ($n = 88$) of the 12-week TLC FIT (8 group meetings + electronic accelerometer + app) versus wait-list control (WLC) group (Aims 2-4). We will evaluate the feasibility of the fitness program, including recruitment, retention, and adherence to the intervention (Aim 2), and test the hypothesis that technology-enhanced intervention will increase AYAs’ muscle strength and cardiorespiratory fitness (Aim 3). We will also explore the effects of the program on secondary outcomes of HRQOL, and fatigue (Aim 4). A randomized wait-list control design is particularly appropriate for this feasibility study, as all recruited individuals receive the intervention, allowing intervention adherence and program satisfaction data to be obtained from all study participants. Such a design can also increase the appeal of random assignment to study participants. The Phase 2 study design is presented in Figure 2.

[figure not shown]

Figure 2. Phase 2 Study Schema

4.1 Procedures

Phase 1. Development of smartphone application

We gathered information about functionality requirements for the smartphone app in our preliminary work with AYA cancer survivors. We will recruit a total of 20 AYA survivors for this phase of the study. We will use individual or small group interviews conducted by the PI or a trained research assistant to gain additional input about desired features for the app. We will also get feedback on mock designs for the app. We will record these interviews and they will be transcribed for analysis by a member of the research team. The exact number of interviews conducted will depend on the data gathered; we will analyze the data as we go and we will stop interviewing when we reach saturation (i.e., no new themes emerge from the data).

Next, we will work with the technology consultants to develop a prototype based on AYA preferences. The exact content of the app will be determined in the development phase but it will reflect the content of the original TLC FIT program (based on Social Cognitive Theory)

and include tailored cancer-specific fitness information (e.g., potential effects of radiation/chemotherapy and issues to consider when exercising based on up-to-date COG guidelines). Users will create a private login. Data from an electronic accelerometer will be directly imported into the app and used to unlock achievement awards. Individuals will set personal goals, monitored in real-time. Instruction videos of the trainer demonstrating exercises will allow for instruction 24/7. A qualified trainer with experience working with adolescents and young adults will be used for this study. Engagement with the app will unlock achievements and there will be optional social support messaging between individuals in the study. The PI and/or trainer will initiate challenges and prompt participants to continue working on goals between sessions. All user data will be continuously stored in an encrypted and cached environment on the device itself. When an internet connection is available, the device will securely transmit the data to our servers for downloading by researchers.

The app will be created using an iterative development process. Product development is broken into logical pieces, prioritized, and completed in iterations. Usability testing is conducted after each piece. Usability testing at this stage involves observation of participants completing defined tasks, time to complete tasks, errors in use, and subjective assessment of satisfaction, ease of learning the app, and memorability of the app.³⁸ This can be done in person or remotely via computer and phone. Usability tests are completed using a rapid iterative procedure, in which design changes are made after receipt of one set of participants' feedback (usually four participants) and then tested with the next set of participants. The app is refined to eliminate issues that impede usability. The final usability tests would include a field trial of using the app for up to one week and providing feedback regarding use in daily life. Having a smartphone is not required to participate; we will loan iPod touches to anyone who does not have a personal smartphone for the duration of the study. We have planned for 12-18 months for total development time. We expect it will take 3-6 months to design and refine the health and cancer-specific content for the app, 3-4 months to design the app, and 3 months to conduct usability testing with the app. Our goal is to minimize frustration with technology. Individual participation may include a one-time interview or usability test (approximately 1-2 hours) or a field trial of using the app for up to a week.

Phase 2: Pilot RCT

Recruitment will occur in waves, such that 10-20 participants will be randomized within cohorts, and each arm will have 5-10 patients at a time. After obtaining informed consent/assent, participants will complete baseline assessments (Time 1) conducted either in group formats or individually as done in our preliminary study. The assessments will be conducted by trained research personnel. Participants will then be randomized to either TLC FIT (8 group sessions + electronic accelerometer + App) or wait-list control (WLC). Randomization will be stratified by cohort (since enrolled in waves) and age (13-17 vs. 18-25). All participants will be asked to complete assessments at Time 2 (~2 months, after the in-person sessions are completed for the TLC FIT group), Time 3 (~3 months; after the full in-person plus app intervention for TLC FIT group), Time 4 (~6 months), and Time 5 (~9 months; after the waitlist control participants receive the intervention). Waitlist control participants will also be asked to complete the objective fitness tests during the last session of the in-person groups; they will be given feedback on their results but no additional monetary compensation for these tests. Assessments and the group fitness program will be conducted in at the Center for Health and Human Performance (directed by Co-Investigator [name]

[name]) at the Institute for Food, Nutrition, and Health on Rutgers Cook Campus in New Brunswick. This is a facility equipped with appropriate equipment and space for group exercise. The trainer will be a qualified professional trainer or member of the Center for Health and Human Performance with appropriate experience and expertise who will be closely supervised by [name] and the PI.

TLC FIT (Technology-Enhanced Intervention): TLF FIT is composed of the group fitness program, use of an electronic accelerometer, private Facebook group and the mobile app. The group fitness program is manualized and will be led by a qualified trainer. The PI will teach the trainer the manualized program and treatment integrity will be evaluated during the program. The group program has four primary components: (1) cancer-specific and general educational modules, (2) physical exercise, (3) goal-setting and self-monitoring, and (4) social support. The original program consisted of eight weekly group sessions; however, participants expressed interest in adding exercise sessions, which would likely increase the impact on participants’ fitness. Therefore, the program is now 8 weekly group sessions lasting 90 minutes each plus 4 weeks of using the app without in-person groups. In-person sessions will consist of approximately 20 minutes of education regarding fitness and administrative tasks, 10 minutes of goal-setting/monitoring, and 60 minutes of instructor-led exercise and cool-down (~30 minutes of aerobic exercise and 30 minutes of muscle strengthening and balance exercises). Exercises are age-appropriate and the intensity of participation is individualized – that is, any exercise can be modified to be more or less strenuous for each participant based on participants’ ratings of perceived exertion as well as any physical limitations due to cancer treatment (such as hip problems). The trainer will have experience in assisting teens and young adults in modifying exercises to a level appropriate to their current fitness and physical abilities. Participants will wear a commercially available electronic accelerometer daily throughout the intervention to self-monitor progress. Data from the accelerometer will be electronically extracted into the app for easy monitoring and sharing of goals/progress. Social support for physical activity will be fostered through group interactions at each session and group messaging within the app and Facebook private groups. During the follow-up period, participants continue to use the app, set physical activity goals, and monitor progress. We will remotely download data regarding app use weekly throughout the intervention and follow-up.

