4.2 Duration of Study

The K07 training grant is a 5-year grant. The app development and refinement (Phase 1) will occur in years 1-2 and the pilot RCT (Phase 2) will occur in years 3-5.

Phase 1: App Development. We have planned for a period of 12-18 months for development, usability testing, and refinement. Information will be gathered from childhood cancer survivors about desired features of the app via interview. During development, feedback about the quality of the program and design elements will be sought. Once a usable app is developed, individuals will be asked to field test the app for a brief period (e.g., a few days or a week, depending on needs identified during development) to evaluate usability in a real-world setting prior to beginning Phase 2.

Phase 2: Pilot RCT. Recruitment will occur in waves, such that cohorts of 10-20 participants will be randomized simultaneously, and each arm will have 5-10 patients at a

time. Following individual consent/assent and completion of a baseline assessment, individuals will be randomized either to the Technology-Enhanced Intervention (TLC FIT) arm or the Waitlist Control (WLC) arm (see Figure 2). Individual data collection will last approximately 9 months, with assessments conducted at approximately 2, 3, 6, and 9 months following randomization. Individuals randomized to the waitlist will receive the intervention after the 6-month assessment. Recruitment and data collection for Phase 2 are expected to span two to three years.

Overview of Study Duration

Study Year	1→				2→				3→				4→				5→			
Quarter	1	2	3	4	1	2	3	4	1	2	3	4	1	2	3	4	1	2	3	4
Phase 1: App Development																				
Training in App Development																				
IRB & study prep																				
App development/Refinement																				
Phase 2: Pilot RCT																				
IRB & study prep																				
Recruitment																				
Data Collection																				
Data Analysis																				
Manuscript Prep																				
Write/Submit Grant																				

5. Patient Selection Criteria

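### Phase 1 field testers may use an exercise-promoting app at home for up to a week, but Phase 1 eligibility does not exclude a known medical contraindication to exercise (minor safety point)

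*Combined protocol and SAP*

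**What the plan says.** **The field trial.** Section 4.1 describes iterative usability testing in small sets ("usually four participants") and then adds: "The final usability tests would include a field trial of using the app for up to one week". Section 4.2 places this step before Phase 2: "Once a usable app is developed, individuals will be asked to field test the app for a brief period". Phase 1 enrols 20 survivors across all its activities. A person may do an interview, a usability test or the field trial, and the number of field testers is not given.

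**The app.** Section 4.1 lists the planned features. They include exercise videos ("Instruction videos of the trainer demonstrating exercises will allow for instruction 24/7"), goals ("Individuals will set personal goals, monitored in real-time"), awards unlocked by accelerometer data, and cancer-specific cautions ("issues to consider when exercising based on up-to-date COG guidelines"). It also says that the content is provisional: "The exact content of the app will be determined in the development phase".

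**Eligibility.** Phase 1 entry (5.1.1 to 5.1.4) needs a cancer diagnosis before age 21, current age 13 to 25, being off treatment, and consent or assent. Its exclusions (5.2.1 to 5.2.3, repeated in 10.1) are language, developmental delay and pregnancy. Medical contraindication to exercise is exclusion 5.2.4, listed under Phase 2 only. The clearance form appears in 10.1 and 10.2, again for Phase 2 only.

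**The concern.** The app is built to get survivors to exercise more. A field tester takes it home and uses it without a trainer present. Someone with a known reason not to exercise satisfies every Phase 1 criterion and could be that tester.

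The protocol itself gives grounds for care. Section 2 reports that almost two-thirds of survivors develop at least one chronic condition and names premature cardiovascular disease as a serious concern. Phase 1 also sets no minimum time off treatment, whereas Phase 2 requires 6 months, so a field tester may be closer to the end of therapy than any Phase 2 participant.

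Only the safety of a few Phase 1 volunteers is at stake. The Phase 2 comparison, its sample size and its endpoints are untouched.

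**Working it through.** No calculation applies. The check compares the two phases and then asks whether another Phase 1 provision does the job of the missing criterion.

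**Step 1: eligibility side by side**

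| Item | Phase 1 | Phase 2 |
|---|---|---|
| Time off treatment | Off treatment, no minimum (5.1.3) | At least 6 months (5.1.7) |
| Number of exclusions | 3 (5.2.1 to 5.2.3) | 5 (5.2.4 to 5.2.8) |
| Contraindication to exercise | Not listed | Excluded (5.2.4) |
| Physician clearance form | Not mentioned | Required before enrolment (10.1, 10.2) |
| Exercise exposure | Home use of the app for up to a week by some participants; none prescribed | Instructor-led sessions, strength and treadmill testing, app use |

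Pregnancy is excluded in both phases, so the Phase 1 list already contains a health-related criterion alongside language and developmental delay.

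**Step 2: other Phase 1 provisions that might screen**

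- *Candidates identified from records (5.6).* The LITE Director and social worker look for potentially eligible patients, but the eligibility rules they apply contain no contraindication item. The same section also provides for people who contact the team themselves.
- *Chart review at accrual (Section 6).* It collects cancer type, treatment history, time since treatment and demographics. It is data collection, not an entry test, and does not list fitness to exercise.
- *Cautions inside the app (4.1).* These inform the user but keep no one out.
- *IRB review (introductory note).* "We will obtain IRB approval for all study procedures and materials prior to their utilization in the project". This is a later review of procedures and materials, not an eligibility rule.
- *Risk statement (10.2).* Phase 1 risk is equated with everyday risk. The supporting sentence refers to the interviews and does not mention the field trial.

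None of these would stop a survivor with a known contraindication from becoming a field tester.

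**Step 3: can the risk be sized?** Three quantities would be needed: the number of field testers, the share with a contraindication, and the amount of exercise that app use would prompt. The plan gives only the usual size of a usability set and the Phase 1 total of 20 for the first, and nothing for the other two. A probability would have to be built on invented inputs, so none is offered.

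**The case against.** The strongest reply is that the two phases have different entry rules because they involve different activities. The Phase 2 form clears a person for a physical activity program with 60 minutes of instructor-led exercise per session, 10-repetition maximum tests and treadmill tests. Phase 1 measures satisfaction, ease of learning and memorability. It sets no exercise dose, fitness test or adherence target. Watching a video or choosing one's own goal is not an instruction to exercise. Some listed functions, such as prompts between sessions, may not run in Phase 1, which has no sessions. The app is to carry cautions, parents consent for minors, and the introductory note says that details are still to be finalised.

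Much of this stands. A reader might infer that Phase 1 breaches the protocol's own safety standard, or that it delivers unsupervised exercise to uncleared patients. The documents support neither reading: 5.2.4 and the form were written for Phase 2, and no exercise is prescribed in Phase 1. A reader might also want to assume a contraindication rate and calculate the chance that at least one tester is affected. The documents supply no rate and do not say how many people will field test, so such a figure would only reflect the assumption. Nor do they justify mandatory physician sign-off. Testers who are not followed in the LITE clinic would need an outside physician's signature for a usability test lasting days.

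What the reply does not remove is the gap itself. The planned app promotes exercise, the tester uses it alone in daily life, and nothing in Phase 1 asks whether that person has been told not to exercise. A sentence stating that the field trial includes no instruction to exercise would clarify its intent, but would not change who receives the app.

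**Conclusion.** The point holds as a minor safety improvement that costs very little. Phase 1 eligibility admits a survivor with a known contraindication to exercise to a field trial of an exercise-promoting app, and no other Phase 1 provision screens that person out. The size of the risk cannot be estimated from the documents. Exposure is at most a week, exercise is optional, and only some of the 20 Phase 1 participants are involved.

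The conclusion assumes that the field-tested version keeps at least some of the exercise features planned in Section 4.1. It also assumes that the field trial is still ahead, as the text is written. If those features are switched off, or the trial is already complete, the point falls away.

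**What to change.** Add one line to the Phase 1 exclusions in 5.2, limited to field-trial participants and in the reporting style of 5.2.2. For example: *for the field trial only, a known medical contraindication to exercise as reported by the patient, a parent or a physician*. Check it against LITE records where the person has them. Carry the same line into the restated criteria in 10.1 so that the two lists agree. Use of the Phase 2 clearance form can be optional.

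Interviews and observed task sessions keep their present entry rules, and the app's features can stay on for the usability test.

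The cost is a short question and, for LITE patients, a look at records that the team already consults to find candidates. An occasional volunteer may be redirected to an interview or task session. Naming the field trial in the Phase 1 risk statement (10.2) and in the adverse event reporting window (Section 8) would be tidy, but it is optional and the fix does not depend on it.
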